So, for example, if a log rank test has p-value $<.008$ at 22 months the stopping rule would dictate termination of the trial with an overall false-positive rate of 5%. Of course in practice, crossing a sequential boundary should trigger further review of other endpoints, and should not be considered as a hard and fast rule for early stopping. Assuming medians of 12 and 16 months in the two treatment groups, a total of 427 events would be expected after 34 months. The "information time" is the fraction of these 427 events expected at each interim analysis. This results in 83% power for detecting a four month difference in median survival of 12 versus 16 months. The calculations are based on a constant failure rate assumption, although the actual analysis will be with a log rank test. The calculations are relevant for the power of a log rank test, if the hazard ratio is the same as the ratio of medians assumed above, i.e., $1.33 = 16 \div 12$. In the actual trial, the exact numbers of events in the "number deaths" column will not be observed at the specified time points. The Lan and DeMets procedure can then be used to determine the appropriate nominal p-values at the times of the interim analyses, depending on the actual numbers of events observed.

The basic analysis of viral activation will involve calculating, within each patient, the ratio of HIV viral load (as measured by RNA PCR copy number) measured one week after initial transfusion, divided by the pre-transfusion copy number. It will be assumed in the following that the logarithm of this ratio is normally distributed, and a two-sample T-test will be used for comparing groups with respect to log ratio. Thus, the endpoint for each patient is the change in viral load on a logarithmic (base 10) scale. Even if the normal distribution is not a good approximation in this case, the T-test is known to be quite robust to violations of this assumption with the sample sizes being considered.

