In pilot data from 10 cases given non-leukoreduced transfusions, the mean change in viral load from pre-transfusion to 7 days post-transfusion was .15 logs (base 10) with a standard deviation of .484 logs, i.e., about a half a power of 10. Six hundred forty cases will provide 97% power for detecting a .15 log difference between the treatments with respect to mean log change in viral load. Even if 50% of cases are missing sufficient data to evaluate this endpoint, (320 cases with data) the power would still be 79%. A treatment difference of .15 logs is a 1.41-fold difference. However, it is felt that a much larger difference, on the order of at least 5-fold difference (.7 logs), would likely be required to have a clinically meaningful effect. Even with a standard deviation of 1.0 logs there is $>93\%$ power for detecting a .7 log treatment difference with a much smaller sample size of 100 patients (50 per group).

Note that the primary clinical endpoint is driving the sample size requirements for the trial rather than the primary laboratory endpoint. This reflects the absence of knowledge about whether a biological effect on viral load would

have any clinical implication for the patient. Thus, the early stopping rule is specifically designed to be based on the clinical endpoint. Even if an early, convincing treatment difference in viral activation is observed, this should not be sufficient for early termination of the trial.

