11.3 Analysis Plans

The primary analysis for the time-to-event endpoint will be the logrank test. The primary analysis for the change in viral load will be the t-test. In other analyses proportional hazards models will be used to adjust treatment comparisons for covariates and to explore the effects of covariates themselves. Short-term changes in viral load will be based on log change from baseline, using two-sample t-tests or a Wilcoxon test if Normal assumptions are violated even after transformations. Covariates will be incorporated using Analysis of Variance. Random effects models will be used to analyze slopes of cytokines, lymphocyte markers and viral load over time. Incidence of individual events will be summarized by calculating number of events per Person-year and compared with Poisson methods. For example, the number of new diagnoses of CMV end organ disease, or diagnoses of CMV progression, will be counted and divided by the number of person-years of followup in order to estimate an incidence rate for CMV events, and compared with Poisson methods. (Note that a single person can have more than one CMV event.) In addition, person-specific incidence rates for each of several event types will be compared with two-sample Wilcoxon tests. The test statistics can be combined into an overall test using methods of Wei and Johnson⁶⁶.

Section 12 -- References

1. Centers for Disease Control: 1993 revised classification system for HIV infection and expanded surveillance case definition for AIDS among adolescents and adults. *MMWR* 1992;41(RR-17):1-19.

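### The primary viral-load test, an unadjusted t-test on log10 change, is valid but gives up modest precision that adjusting for baseline and strata would recover

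*Protocol*

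**What the plan says.** Change in HIV viremia from before the first transfusion to one week after it is the second of two primary objectives (Protocol 2.1.2). Section 11.2 sets the scale: "Thus, the endpoint for each patient is the change in viral load on a logarithmic (base 10) scale". It also sets the test: "a two-sample T-test will be used for comparing groups with respect to log ratio". Section 11.3 confirms it: "The primary analysis for the change in viral load will be the t-test".

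No covariate is part of that primary test. Section 4.2 stratifies randomization by CD4 (or total lymphocyte) count and by CMV disease, but neither factor enters the comparison. Later in 11.3, short-term viral-load changes are to be analysed "using two-sample t-tests or a Wilcoxon test if Normal assumptions are violated even after transformations", and analysis of variance is named as the way to bring in covariates. The covariates are not listed, and this is not presented as the primary analysis. A baseline-adjusted measure, an area under the curve, appears only among the secondary objectives (2.2.11).

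The sizing rests on pilot data from 10 patients: "the mean change in viral load from pre-transfusion to 7 days post-transfusion was .15 logs (base 10) with a standard deviation of .484 logs". From this, 11.2 concludes: "Six hundred forty cases will provide 97% power for detecting a .15 log difference between the treatments". If half the cases cannot be evaluated, it gives 79%.

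**The concern.** The pre-transfusion value must exist for a patient to have a change score at all, and the strata must be known before randomization. Everything needed for an adjusted analysis is therefore already planned.

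A change score amounts to assuming that week-1 log10 RNA moves one-for-one with the pre-transfusion value. If the true slope is below 1, as it is with equal variances and imperfect correlation, two things follow. The comparison is noisier than it need be. And if one arm happens to start higher, part of that difference carries into the treatment contrast.

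The stake is efficiency and conditional accuracy on a primary objective, chiefly in the case the protocol itself considers, where only half the patients have usable data.

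**Working it through.** **Inputs.** SD of log10 change 0.484, difference 0.15, and 640 or 320 evaluable patients (320 or 160 per arm), all from 11.2. Two-sided alpha of 0.05 is stated for survival and assumed here for viral load. The cross-sectional SD of log10 viral load, σ, is not in the protocol, so I assume 0.6, 0.8 and 1.0, with equal variances before and after transfusion.

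**Step 1: the protocol's own figures.** SE = SD × √(2/n per arm); power ≈ Φ(difference/SE − 1.96).
- 320 per arm: SE = 0.484 × √(2/320) = 0.0383; 0.15/0.0383 = 3.92; power 97.5% (stated 97%).
- 160 per arm: SE = 0.484 × √(2/160) = 0.0541; 0.15/0.0541 = 2.77; power 79.2%, or 78.9% by noncentral t (stated 79%).
- 0.7 log, SD 1.0, 50 per arm: SE = 0.200; 0.7/0.2 = 3.5; power 93.8%, or 93.4% by noncentral t (stated over 93%).

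All three reproduce.

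**Step 2: effect of baseline adjustment.** With equal variances, Var(change) = 2σ²(1 − r), so r = 1 − 0.484²/(2σ²). The ANCOVA residual variance is σ²(1 − r²). Dividing the second by the first gives a ratio of (1 + r)/2. For example, at σ = 0.6, r = 1 − 0.2343/0.72 = 0.675 and the ratio is 1.675/2 = 0.837.

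| Assumed σ | r | Variance ratio | Adjusted SD | Power, 320 evaluable | Power, 640 evaluable |
|---|---|---|---|---|---|
| t-test on change | – | 1 | 0.484 | 79.2% | 97.5% |
| 0.6 | 0.675 | 0.837 | 0.443 | 85.8% | 99.0% |
| 0.8 | 0.817 | 0.908 | 0.461 | 82.9% | 98.4% |
| 1.0 | 0.883 | 0.941 | 0.470 | 81.5% | 98.1% |

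The inverse ratios, 1/0.837, 1/0.908 and 1/0.941, mean that the t-test needs about 19%, 10% or 6% more patients for the same precision.

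**Step 3: chance baseline imbalance.** A baseline difference D between arms shifts the change-score contrast by (1 − r)D in size. Take a large chance imbalance, D = 1.96 × σ × √(2/n).
- 160 per arm: 0.325 × 0.131 = 0.043 log at σ = 0.6; 0.117 × 0.219 = 0.026 log at σ = 1.0.
- 320 per arm: 0.325 × 0.093 = 0.030 log at σ = 0.6; 0.117 × 0.155 = 0.018 log at σ = 1.0.

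The largest of these is 0.043/0.15 = 29% of the difference used for power, but 0.043/0.7 = 6% of the difference that the protocol regards as clinically meaningful.

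**Step 4: simulation check.** This used 160 per arm and 4,000 replicates per setting. At σ = 0.5, 0.7 and 1.0, power for the t-test against ANCOVA was 78.0% against 88.5%, 78.4% against 83.0%, and 77.2% against 80.1%. Type I error was 4.5–5.0% for the t-test and 5.0–5.4% for ANCOVA, so both hold the nominal level.

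The gain from adding the strata cannot be quantified from the protocol.

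**The case against.** The strongest reply is that this is a choice between two valid analyses. Much of it stands:

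- Baseline is not ignored. Each patient's value is subtracted on the log scale, and on the r values above only about 12% to 32% of any chance imbalance remains.
- Covariate adjustment by analysis of variance is already foreseen. Naming the covariates would be ordinary detail for an analysis plan.
- At the planned 640 patients the gain is negligible. The protocol says that a difference "on the order of at least 5-fold difference (.7 logs), would likely be required to have a clinically meaningful effect", and it has over 93% power for that with 100 patients. It also says that survival, not this endpoint, drives the sample size.
- The 0.484 comes from 10 patients and σ is assumed, so the size of the gain is uncertain.
- ANCOVA on evaluable pairs does not bring back missing patients or explain why they are missing.

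What the reply does not remove is that the protocol itself fixes the unadjusted test as primary, when a more precise one uses data already in hand.

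On the Wilcoxon test, a reader might infer that the primary test will be picked after seeing the data and so has no fixed error rate. The text does not establish this. The primary test is first stated without condition; the conditional sentence follows a turn to other analyses and can be read as covering the many other short-term comparisons. It can also be read as including the one-week change, so the wording should be made clear.

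**Conclusion.** The point holds as a modest and free gain in efficiency. Under the stated assumptions (σ from 0.6 to 1.0, equal variances, SD of change 0.484), baseline adjustment lowers the variance by about 16% to 6%. It adds roughly 2 to 7 power points for 0.15 log with 320 evaluable patients, and 1 to 2 points with 640.

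A reader might go further and infer that the t-test is biased, or that leaving out covariates inflates the false-positive rate. The documents do not support that. Regression to the mean acts on both randomized arms alike, and omitting the strata makes the test conservative at worst. The protocol's power figures are correct for the test it names.

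**What to change.** In 11.2 and 11.3, name as the primary viral-load analysis an ANCOVA of week-1 log10 HIV RNA on treatment arm, pre-transfusion log10 HIV RNA, the CD4/total lymphocyte stratum and the CMV-disease stratum. Keep the two-sample t-test on log10 change as a supportive analysis. State that, for this primary endpoint, the conditional Wilcoxon test is a sensitivity analysis only.

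The power figures in 11.2 can stay, described as those of the unadjusted test and therefore slightly conservative for the adjusted one. The cost is wording: sample size, visits and specimens do not change. The edit should be made before any viral-load data are compared by arm.

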Appendix II

Karnofsky Performance Scale

Able to carry on normal activity; no special care is needed	100	Normal; no complaints; no evidence of disease.
	90	Able to carry on normal activity.
	80	Normal activity with effort; some signs or symptoms of disease.
Unable to work, able to live at home and care for most personal needs; a varying amount of assistance is needed.	70	Cares for self, unable to carry on normal activity or to do active work.
	60	Requires occasional assistance but is able to care for most needs.
	50	Requires considerable assistance and frequent medical care.
Unable to care for self; requires equivalent of institutional or hospital care; disease may be progressing rapidly.	40	Disabled; requires special care and assistance.
	30	Severely disabled; hospitalization is indicated, although death is not imminent.
	20	Very sick; hospitalization necessary; active supportive treatment is necessary.
	10	Moribund; fatal processes progressing rapidly
	0	Dead
